### *Rationale for using the EQ-5D to measure Utility Values*

The European Quality of Life-5 Dimensions (EQ-5D) is a preference-based utility index algorithm will be used to calculate each subject's utility index (13). This instrument will be collected at baseline and 3 months. The EQ-5D has 5 attributes (mobility, self-care, usual activities, pain/discomfort and anxiety/depression) with 3 levels each for a possible 243 unique health states. Using the scoring function based on time-tradeoff method we will compare change in QALYs between the two treatment groups. We are choosing to use a general scale to calculate change in utilities (rather than condition-specific) to allow for comparison of cost-effectiveness results with other interventions and diseases, and this instrument has been validated in women with pelvic floor disorders.

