### 6. Study Timelines

Based on current clinic volume in the UNM division of Urogynecology, we estimate recruitment of up to 75 patients would be feasible over a 12 month period. A review of our clinic calendar revealed in 1 months' time, the urogynecology division typically sees 10-20 patients who would meet criteria for our study. Assuming 50% enrollment, we will be able to recruit our projected number of patients in 12 months. Additionally, as subjects will be followed for 3 months after randomization, we expect it may take up to 15 months to collect 3 month follow up data. We estimate that data analysis and composition of the manuscript will take an additional 10 months.

Timeline	July 2018- Oct 2019	Nov 2019-Feb 2020	Mar 2017-May 2020
Subject recruitment, therapy, through 3 month follow up	←→		
Data analysis		←→	
Manuscript preparation		←→	

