#### Outcome Measures:

1. **Pelvic Organ Prolapse Quantification (POP-Q):** This is a validated scale adopted by IUGA/ICS and described in their 2010 joint report. It aims to measure the degree of POP where the hymen is the fixed point of reference for description. (5)
2. **Modified Oxford grading system:** This applies a 6-point scale to rate the muscle strength of the pelvic floor where, strength is as follows:  
0 = no contraction; 1 = flicker; 2 = weak; 3 = moderate; 4 = good; 5 = strong (6)
3. **The Pelvic Organ Prolapse/Incontinence Sexual Questionnaire, 12 (PISQ-12):** This is a brief validated, reliable and responsive measure of women's sexual function in those with pelvic floor disorders. (7)
4. **Incontinence Severity Index (ISI):** This is a validated questionnaire that has been shown to correlate well with pad weighing tests. (8)
5. **Patient's Global Impressions of Improvement (PGI-I):** This is a validated 1-item questionnaire rating specific condition as perceived change in her condition in response to therapy for SUI. (9)
6. **The International Consultation Incontinence Questionnaire-Short Form (ICIQ- SF)** This validated scale is a condition-specific assessing QOL of women with urinary incontinence. The most recent Cochrane review on Biofeedback recommends using this scale in trials using biofeedback for urinary incontinence. (10,11)
7. **Female Sexual Function Index (FSFI):** A brief questionnaire measure of sexual functioning in women that assesses arousal, orgasm, satisfaction and pain. (12)
8. **European Quality of Life-5 Dimensions (EQ-5D):** Preference-based utility index algorithm used to calculate each subject's utility index and compare change in QALYs between treatment groups (13).
9. **Overactive Bladder Questionnaire- short form (OAB-q SF):** Symptom bother scale that captures the full spectrum of OAB symptoms and health related quality of life (14).

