### **Comparative Cost Analysis**

The cost analysis will be conducted from a societal and patient perspective and will be expressed as incremental cost required to produce one additional unit of quality-adjusted life year (QALY). Data on each subject's use of medical and non-medical resources related to stress urinary incontinence care will be collected during the follow up period. Direct and indirect costs of care in the physical therapy group will be compared to the at home biofeedback group. We plan to capture incremental direct health care, direct non-medical, and indirect resource use related to study interventions and incontinence care using surveys.

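### The cost-per-QALY endpoint has no stated rule for turning two EQ-5D readings into QALYs, and no fixed adjustment for baseline utility

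*Combined protocol and SAP*

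**What the plan says.** All references are to the combined protocol and SAP.

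- Section 7 lists cost effectiveness among the secondary endpoints. Section 13, Comparative Cost Analysis, says the result will be "expressed as incremental cost required to produce one additional unit of quality-adjusted life year (QALY").
- Section 13, Rationale for using the EQ-5D, gives the timing: "This instrument will be collected at baseline and 3 months". It then says: "Using the scoring function based on time-tradeoff method we will compare change in QALYs between the two treatment groups".
- The same paragraph explains the choice of instrument: "We are choosing to use a general scale to calculate change in utilities (rather than condition-specific"), so that cost-effectiveness results can be set beside those for other conditions.
- Section 12, Outcome Measures, says the EQ-5D is "used to calculate each subject's utility index and compare change in QALYs between treatment groups".
- The opening paragraph of Section 13 gives the general rule for continuous variables, the t-test. A multivariable analysis follows only if the arms are found to differ at baseline.
- Section 6 says "subjects will be followed for 3 months after randomization". Section 12 lets the follow-up visit of a woman who starts physical therapy late be timed from her first therapy session.

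**The concern.** A time-tradeoff scoring function turns an EQ-5D profile into a utility. A QALY is utility multiplied by time. The plan goes from one to the other without the multiplication: it gives no area-under-the-curve rule, no interpolation rule and no horizon. It also uses *change in QALYs* and *change in utilities* as if they were the same quantity. Two analysts could follow the text in good faith and report cost-per-QALY figures several-fold apart.

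A second problem arises even if the conversion is done properly. A QALY total built from two readings contains the baseline reading. If the arms differ at baseline by chance, the difference enters the QALY comparison directly. The plan adjusts only when a baseline difference is noticed. It does not say what counts as one, and it does not tie the rule to the cost analysis.

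At stake is whether the cost-per-QALY result can be reproduced and set beside results for other conditions, which is the plan's own reason for choosing a generic instrument.

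**Working it through.** **Inputs.** From the documents: two EQ-5D readings, nominally 3 months (0.25 year) apart, and 21 evaluable women per arm (Section 5). The plan states no utility difference, QALY difference or cost per QALY, so there is no figure of its own to reproduce. Its count of 243 health states is correct (3^5 = 243). Utility SD, utility difference and cost difference are assumptions, marked as such.

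**1. Size of the error if utility change were used as QALYs.** Let D be the between-arm utility difference at 3 months, with equal baselines. The QALY difference is the area under the utility-difference curve.

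| Path of the utility difference | QALY difference | Understatement of cost per QALY |
|---|---|---|
| Linear over 3 months | 0.25 × (0 + D)/2 = D/8 | 8-fold |
| Full effect at once | 0.25 × D = D/4 | 4-fold |
| Linear to a plateau at 1 month | 0.208 × D | 4.8-fold |
| Effect in the last month only | D/12 | 12-fold |
| Area under the curve actually computed | as above | none |

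If the interval from baseline to follow-up is m months and the change is linear, the factor is 24/m: 6.0 at 4 months and 4.8 at 5 months.

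Illustration with an assumed cost difference of USD 300:

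- Assumed D = 0.02: 300/0.02 = 15,000 with no time weighting; 300/(0.02/8) = 120,000 with linear change; 300/(0.02/4) = 60,000 with immediate effect.
- Assumed D = 0.05: 6,000, 48,000 and 24,000 respectively.

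**2. Baseline imbalance if area under the curve is used without adjustment.** The standard error of the chance baseline gap is SD × sqrt(2/21) = 0.309 × SD. The baseline term of the trapezoid multiplies the gap by 0.25/2 = 1/8.

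| Assumed utility SD | SE of baseline gap | QALYs through the baseline term |
|---|---|---|
| 0.10 | 0.031 | 0.004 |
| 0.15 | 0.046 | 0.006 |
| 0.20 | 0.062 | 0.008 |

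For comparison, the assumed effects above are worth 0.02/8 = 0.0025 and 0.05/8 = 0.006 QALY under linear change. If all 75 permitted women were enrolled and retained (37.5 per arm), the SE would be 0.231 × SD, which gives 0.023 to 0.046, or 0.003 to 0.006 QALY. These figures count the baseline reading only. If the two readings are positively correlated, part of the gap persists at 3 months and adds to them.

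**3. What adjustment removes.** Suppose the SD is the same at both readings and the correlation is r. The unadjusted QALY variance is proportional to 2 + 2r. The variance after regression on baseline utility is proportional to 1 − r². The ratio is (1 − r²)/(2 + 2r) = (1 − r)/2, so for any r of zero or more the variance falls by at least half.

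**4. Unequal observation time.** If QALYs are accumulated to each woman's actual visit, an extra month adds u/12 QALY for a woman with utility u, whatever the treatment does. Only the physical-therapy arm has the late-start rule, so this could differ by arm.

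**The case against.** The strongest reply is that the plan names QALYs each time it names the quantity compared between arms. The reference to utilities sits in a sentence about why a generic scale was chosen, and does not define a denominator. A change in QALYs compared between groups can naturally mean incremental QALYs, which two readings do support. All of that stands. A reader might infer that the plan divides cost by the raw utility change and so will report a figure 8-fold too low. The documents do not say so, and if area under the curve is computed in practice the factor is 1.

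The two problems also belong to different readings. A utility change already has baseline subtracted, so the imbalance described here does not enter it. An unadjusted area-under-the-curve total has no time-weighting error. They should not be added together.

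A reader might also infer that baseline differences are ignored altogether. Section 13 does provide for a multivariable analysis if such differences appear. But that rule has no defined trigger, names no covariates and depends on the observed data, so it does not replace a fixed adjustment.

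Finally, a reader might infer that correction makes home biofeedback look worse. Aim 2 expects it to be cheaper with similar success. If it is cheaper and no worse in QALYs it dominates, and rescaling the denominator changes nothing. If it is cheaper with slightly fewer QALYs, correct scaling raises the saving per QALY lost. The direction therefore depends on the signs of both differences. Baseline imbalance is another matter: when the true QALY difference is near zero, it can change the sign itself.

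**Conclusion.** The point holds as an unspecified conversion plus an inadequate adjustment rule. It is not a demonstrated error in the result.

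- **Conversion.** The denominator cannot be reproduced from the text. The exposure is about 8-fold under linear change, equal baselines and exactly 0.25 year, roughly 4- to 12-fold for other paths over 3 months, and nil if area under the curve is used. Taken alone, this is close to a missing detail.
- **Baseline adjustment.** This is the firmer part. With area under the curve and no fixed adjustment, chance imbalance contributes a standard error of about 0.004 to 0.008 QALY through the baseline term, assuming a utility SD of 0.10 to 0.20 and 21 per arm. That is as large as, or larger than, many of the effects one might assume, and a baseline reading already collected would remove it.

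The ICIQ-SF primary endpoint is not affected.

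**What to change.** In Section 13:

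1. Define each woman's QALYs as the trapezoid area under her EQ-5D utility curve, with time in years, over a stated horizon common to both arms. Count costs over the same horizon.
2. State how women whose physical therapy starts late are handled. A fixed 0.25 multiplier would be wrong for a woman whose two readings are more than 3 months apart, unless her utility at the common horizon is interpolated. Reconcile the follow-up clocks in Sections 6 and 12.
3. Estimate the between-arm QALY difference by regression of QALYs on arm and baseline utility. Prespecify this and apply it whether or not a baseline difference is seen. Use the estimate in the cost-per-QALY result.
4. In Section 13 (EQ-5D rationale) and Section 12 (Outcome Measures), replace *change in QALYs* with *difference in QALYs between groups*.

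The cost is a few sentences written before analysis. Both EQ-5D readings are already in the schedule, so no new data or visits are needed. The reported ratio may move in either direction, depending on the signs of the cost and QALY differences.

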## **14. Provisions to Monitor the Data to Ensure the Safety of Subjects**

There is no DSMB that will be monitoring safety of these procedures. PFPT is a common treatment modality for SUI and standard of care. The biofeedback device is FDA approved and

**PROTOCOL TITLE: SQEASI: Systematized Quality Exercise Alternatives for Stress Incontinence**

we anticipate minimal safety concerns from use. Vaginal bleeding, pelvic muscle pain, bacterial vaginosis and pelvic pain could conceivably be caused by use. Additionally, we will keep track of adverse events and ask patients about adverse events at the 3 month time point. Because neither of the studied treatments are experimental or associated with above average risk we do not anticipate any adverse events. Participants will have access to a 24/7 phone number to reach research or clinical staff with concerns. All adverse events will be recorded and reported to the study PI.

We do not anticipate any conditions that would trigger a suspension or termination of the research.

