Randomization assignment will be generated by computer based randomization table and assigned by a research coordinator not otherwise involved in the study. Assignments will be kept in sealed opaque envelopes numbered sequentially. On the day of the patient's clinic visit, after signing consent and deciding to participate, the research coordinator will bring the next envelope in the sequence will be opened, randomizing the patient to PFPT or home biofeedback. The therapy allocation will then be carried out.

The biofeedback group will be given a PeriCoach® biofeedback device, which has a Bluetooth connection to a smartphone, free of charge. The smartphone application will be uploaded during the visit and linked to the device to ensure the patient understands how to

PROTOCOL TITLE: *SQEASI: Systematized Quality Exercise Alternatives for Stress Incontinence*

install the program. An information sheet with recommendation for exercise frequency will be given at the time of enrollment to provide recommendations for use. All participants will start as a beginner in the program and works up to a maintenance level. At the end we expect they will be doing 15 exercises, 3 times per day per manufacturer's instructions. 2 weeks following enrollment, these patients will be called to ensure they understand how device functions and are not having technical difficulties. When the patient returns for the 3 month follow up the smartphone app will be reviewed as the app records how often the patient performs the exercises. If that is not available, we will have the patient self-report her exercise frequency.

For patients randomized to physical therapy, PFPT will be scheduled for 4 sessions over 3 months, as is common practice for patients with SUI. These patients will receive instructions on how to engage their core, contract their vaginal muscles, as well as recommendations for home exercises to be performed for 3 sessions per day. The first session will be to establish the patient's baseline abilities with follow up sessions to reinforce instructions, performance of exercises and to ensure the patient is improving. Patient compliance of attending PT sessions will be recorded, as will the amount each patient spends in co-pays per session. After 3 months, regardless of the number of appointments the patient has attended, she will return for a follow up visit to assess how well she is doing.

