Three months after starting active treatment, all participants will have a return visit to discuss progress, which is consistent with our standard care for these patients. If the participant had a delay in starting PFPT, the follow up visit will occur 3 months after first PT appointment. At the 3 month visit the patient will complete the ISI, ICIQ-SF, EQ-5D, OAB-q SF, PISQ-12, FSFI, and PGI-I. We will also ask the patient which treatment she would prefer if given the option, the level of satisfaction she has with the current treatment, and if she is planning any future surgical procedures or treatment for her stress incontinence. A physical exam will assess pelvic floor strength using the Modified Oxford Grading Scale and a cough stress test will be performed. If the patient is unable to return to clinic, a member of the research team will call the patient to administer the surveys over the phone. If unable to contact the patient 3 times, we will discontinue attempts and the patient will be considered lost to follow up.

Table 1: Outcomes collected at various time points

	Baseline	3 months
Demographic and medical history	X	
ISI	X	X
Revised Oxford Scale	X	X
ICIQ-SF	X	X
EQ-5D	X	X

FSFI	X	X
OAB-q SF	X	X
PISQ-12	X	X
PGI-I		X
Follow up Questionnaire		X

Our primary outcome is changes in QOL at 3 months after treatment initiation as measured by the ICIQ-SF. It is our standard of care to see patients back at 3 months following SUI treatment initiation to assess for continued leakage and offer further conservative or surgical management. Therefore, as part of a secondary aim we will assess sexual function, compliance with treatment between groups, preference between 2 options, and desire for further treatment at this 3 month time point.

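### Adverse events are actively asked about only at 3 months, and scheduled contact before then differs by arm, so events may be unequally ascertained or learned of late

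*Combined protocol and SAP*

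**What the plan says.** Section 14 names possible harms of the device: "Vaginal bleeding, pelvic muscle pain, bacterial vaginosis and pelvic pain could conceivably be caused by use". On collection it says "we will keep track of adverse events and ask patients about adverse events at the 3 month time point". It adds that "Participants will have access to a 24/7 phone number to reach research or clinical staff with concerns" and that "All adverse events will be recorded and reported to the study PI".

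Section 12 sets the contacts before 3 months. In the physical therapy arm, "PFPT will be scheduled for 4 sessions over 3 months". In the biofeedback arm, "2 weeks following enrollment, these patients will be called to ensure they understand how device functions and are not having technical difficulties". No adverse-event question is specified at either kind of contact. Table 1, which lists what is collected at baseline and at 3 months, has no adverse-event row.

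A woman who cannot attend at 3 months is phoned for the surveys, with adverse events not mentioned. Then: "If unable to contact the patient 3 times, we will discontinue attempts and the patient will be considered lost to follow up".

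Section 7 states that there are no safety endpoints, Section 33 and the Medical Devices checklist say device safety is not under evaluation, and Section 13 plans no comparison of adverse events.

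**The concern.** The events that Section 14 names can be early and short-lived. A single question about 3 months after treatment starts relies on recall for such events, unless the woman has phoned in. A woman who stops because of discomfort and then withdraws may leave before the question is put, because no exit question is specified. Section 15 says reasons for withdrawal will be documented, but the examples it gives are failed eligibility and declined enrolment.

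The opportunities to mention a symptom in passing also differ by arm. Section 14 records every event however it surfaces, so the final list will mix answers to a common question with reports that arose through unequal contact. At stake are how soon the study learns of a problem and how far any adverse-event counts shown by arm can be trusted. There is no data and safety monitoring board, so recording events and reporting them to the principal investigator is the oversight the plan describes.

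**Working it through.** The documents give no adverse-event rate and no safety sample size, so there is no stated figure to reproduce. The check is a count of contacts, followed by an illustration of what that count could do.

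**1. Contacts before the 3-month visit (Sections 8, 12, 14 and 22)**

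| | PFPT | Home biofeedback |
|---|---|---|
| Scheduled contacts | up to 4, in person | 1, by phone at 2 weeks |
| Stated purpose | baseline assessment, then reinforcement and progress | device function, technical difficulties |
| Adverse-event question specified | no | no |
| Patient-initiated line | yes | yes |
| Adverse-event question at 3 months | yes | yes |

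Four is a maximum. The first session sets the baseline, so at most 4 − 1 = 3 sessions can follow the start of therapy. Attendance is not assured either: the 3-month visit goes ahead however many sessions were attended, and Section 22 allows 0 to 4 therapy trips.

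**2. What unequal contact could do to detection**

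Every input here is an assumption, because the documents supply none:
- r: chance that an event is reported at the 3-month question, 0.5 to 0.9.
- v: chance that it is noted at any one therapy session, 0 to 0.3, with two sessions after onset.
- c: chance that it is noted on the 2-week call, 0 to 0.3, with half of events occurring before the call.
- True risk 20% in each arm, 25 women per arm: 25 × 0.20 = 5 true events per arm.

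Share detected, PFPT: 1 − (1 − r)(1 − v)².
Share detected, home: 0.5 × [1 − (1 − r)(1 − c)] + 0.5 × r.

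Example with r = 0.5, v = 0.3, c = 0. PFPT: 1 − 0.5 × 0.49 = 0.755, or 3.775 of 5 events. Home: 0.5, or 2.5 of 5. Ratio: 2.5 / 3.775 = 0.66.

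| r | v | c | PFPT, of 5 | Home, of 5 | Home/PFPT |
|---|---|---|---|---|---|
| 0.5 | 0.3 | 0 | 3.775 | 2.500 | 0.66 |
| 0.5 | 0.3 | 0.3 | 3.775 | 2.875 | 0.76 |
| 0.5 | 0 | 0 | 2.500 | 2.500 | 1.00 |
| 0.5 | 0 | 0.3 | 2.500 | 2.875 | 1.15 |
| 0.9 | 0.3 | 0 | 4.755 | 4.500 | 0.95 |
| 0.9 | 0 | 0.3 | 4.500 | 4.575 | 1.02 |

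The assumed 20% risk and the 25 women cancel from the ratio. The phone line is left out; if both arms used it equally, it would pull the ratio toward 1. The result turns on whether therapy sessions or the 2-week call feed adverse-event reports, which the documents do not say.

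**3. What a comparison of arms could show even with perfect recording**

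For an assumed 20% against 10% with 25 per arm, two-sided 0.05, normal approximation:
- Standard error under no difference: √(2 × 0.15 × 0.85 / 25) = 0.101.
- Standard error under the difference: √((0.1 × 0.9 + 0.2 × 0.8) / 25) = 0.100.
- Power: Φ[(0.10 − 1.96 × 0.101) / 0.100] = Φ(−0.98) ≈ 0.16.

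If no events are seen in 25 women, the one-sided 95% upper limit is 1 − 0.05^(1/25) = 0.113, about 11%.

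**The case against.** The strongest reply is that nothing the plan sets out to estimate is harmed. There are no safety endpoints and no adverse-event analysis, and at this size a comparison would be uninformative anyway. The 3-month question is the same in both arms, and a woman with pain or bleeding can phone at any hour. Section 18 says the device carries the same risks as therapy, so harm is not a concern of one arm only. All of this stands. It limits the point to participant safety and the quality of reporting, but it does not remove it: the line works only if the woman calls, and earlier learning of events needs no comparison of arms.

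Two stronger readings are tempting and should be resisted.

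- A reader might infer that early harms are under-detected in the home arm, which would flatter home biofeedback. The documents do not support this. For therapy sessions, Section 12 says that attendance and co-pays are recorded and does not mention symptoms; only the home arm has a scheduled call from the study. The direction is open.
- A reader might apply the 20% dropout figure and conclude that 25 × 0.20 = 5 women per arm are never asked. That figure is a sample-size allowance, not a forecast of unreachable women, and women who miss the visit are phoned. The same 5 would also apply to each arm, so it could not show a difference between them.

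**Conclusion.** The point holds in a limited form. Active enquiry is specified once, at 3 months. Earlier events rely on patient-initiated reports, and scheduled contact before then is up to 4 sessions against 1 call. Adverse events may therefore be unequally ascertained, and early transient events, or events in women who stop or withdraw, may be missed or learned of late. The range of 0.66 to 1.15 illustrates possible size under assumed detection chances; it is not an estimate, and the text fixes neither size nor direction. The primary ICIQ-SF analysis, the sample size and every planned endpoint are unaffected. This is a cheap improvement worth making for participant safety and for the credibility of any counts later shown by arm.

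**What to change.** - Write one short scripted prompt that names the Section 14 events, and add it to the existing 2-week biofeedback call.
- Give the same prompt to PFPT women at a matched point, for example the nearest therapy session. Because therapy can start late, count the match from the start of treatment.
- Use the same prompt at 3 months in both arms, and state that the phone fallback includes it.
- Ask it at the last contact with any woman who stops treatment or withdraws, and record whether an event was the reason.
- Add adverse events to Table 1 at these time points. Positive answers then go to the principal investigator under the reporting already promised in Section 14.
- Record solicited and spontaneous events separately. If counts are reported by arm, describe the solicited ones without a formal test.

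The cost is a few minutes on a call already scheduled, a short item at a therapy session, one form, and slightly more events recorded. No visit is added. Asking by phone in one arm and in person in the other leaves a small difference in mode; a brief call to both arms would remove it at the price of one extra call per PFPT woman.
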